TAT	Thrombin-antithrombin
TB	Tuberculosis
TCAE	Terminology Criteria for Adverse Events
Tid	Three times daily
TNF	Tumor Necrosis Factor
ULN	Upper Limit of Normal
UNOS	United Network of Organ Sharing
WHO	World Health Organization
y.o.	Years old

Study Definitions

Full graft function: Islet transplant recipients will be considered to have full islet graft function if they are insulin independent (as defined below).

Graft failure: Islet allograft failure will be defined as absence of insulin production by transplanted islets, as evidenced by c-peptide < 0.3 ng/mL. This will be determined by (1) c-peptide < 0.3 ng/mL on random testing, followed by (2) c-peptide < 0.3 ng/mL at baseline, and at 60 and 90 minutes after MMTT. Participants with graft failure do not need to complete the day 75 metabolic assessments.

Insulin-independent: Islet transplant recipients will be considered insulin-independent with full islet graft function if they are able to titrate off insulin therapy for at least 1 week and all of the following criteria are met:

- One HbA1c level, one fasting serum glucose level, and a Mixed Meal Tolerance Test are documented within the visit window (e.g. 70-80 days at Day 75) and 7 consecutive days of blood sugar and insulin readings are documented within ± 7 days of the visit window (e.g. 63-87 days at Day 75);
- HbA1c $\leq 6.5\%$ or a $\geq 2.5\%$ decrease from baseline (within 91 days prior to transplant);
- Fasting capillary glucose level should not exceed 140 mg/dL more than three times in 7 consecutive days (fasting is defined as 1st blood sugar reading of the day not noted as post-prandial or bedtime);
- Post-prandial serum glucose ≤ 180 mg/dL at 90 minutes during the MMTT;
- Fasting serum glucose level ≤ 126 mg/dL; if the fasting serum glucose level is > 126 mg/dL, it must be confirmed in an additional one out of two measurements;
- At least one MMTT fasting or stimulated c-peptide ≥ 0.5 ng/mL.

Insulin dependent: Islet transplant recipients who do not meet the criteria for insulin independence will be considered insulin-dependent.

Intensive diabetes management: Self-monitoring of glucose values no less than a mean of three times each day averaged over each week and by the administration of three or more insulin injections each day or insulin pump therapy.

Partial graft function: Islet transplant recipients who do not meet criteria for insulin independence, but have either a basal or stimulated c-peptide level ≥ 0.3 ng/mL (0.1 nmol/L).

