1.2 Rationale for Selection of Study Population

Individuals with T1D and a successful kidney allograft are particularly appropriate candidates for an islet transplant procedure because they are already obligated to chronic life-long immunosuppression. Thus, the nominal risk of the islet transplant procedure itself is minimal compared to the risks for non-uremic patients with diabetes receiving new immunosuppression in addition to the transplant procedure⁷⁵⁻⁷⁷. Also relevant is the preliminary evidence from uncontrolled studies suggesting that transplanted islets in patients who have already received a kidney transplant may provide beneficial renal and cardiovascular effects⁷⁸⁻⁸⁰.

Critical in IAK transplantation is avoiding disruption of the function of a successful life-saving kidney transplant. For this reason, only kidney recipients > 3 months post-transplant who demonstrate stable graft function and the absence of rejection episodes in the previous three months will be considered for enrollment. This will avoid the early post-transplant period in which complications and allograft rejection are most common. Similarly, the most appropriate immunosuppression must be selected to avoid islet and kidney graft rejection as well as deleterious side effects to either the islets or the kidney from the medications.

Patients will also be selected based on inadequate glucose control following a period of diabetes management by an experienced clinician. Such management should consist of a target HbA1c levels of < 6.5% as suggested by the ACE Consensus Statement on Guidelines for Glycemic Control⁸. Following a period of ≥ 4 months on this therapy, only patients who evidence continued inadequate glucose control characterized by either HbA1c $\geq 7.5\%$ or HbA1c < 7.5% but with severe hypoglycemic episodes (≥ 1 severe episode) as defined by the DCCT trial (and Clarke hypoglycemia score > 4) will be considered for transplant. This approach will target the group of post-renal transplant diabetics most likely to benefit from islet transplantation.

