1.5.1.3 Sensitization of the Recipient to Donor Antigens

As with any allogeneic transplant, the recipient of an organ transplant may become sensitized against donor antigens. Islet transplant recipients who lose their islet graft due to allorejection may develop alloantibodies directed at donor alloantigens. Data on the development of cytotoxic antibodies against donor histocompatibility leukocyte antigens (HLA) in islet allotransplant recipients with failing grafts have been communicated from several islet transplant centers¹⁰³⁻¹⁰⁷. Once an islet graft fails in islet alone patients, immunosuppressive medicines are usually stopped which can lead to the development of antibodies against the transplanted tissues. IAK patients are also at risk for developing antibodies against the transplanted islet tissue. The exact chance of developing these antibodies in islet-kidney transplant patients is not known, but it is thought to be less than in patients who receive islet alone transplants, since patients with kidney transplants will continue taking maintenance immunosuppressive medications even if the islet graft fails. This is also supported by data from whole organ pancreas transplantation¹⁰⁸. It is estimated that overall risk of significant levels of additional sensitization from the islet graft is approximately 5-10% in IAK patients who continue on maintenance immunosuppressive medications (unpublished data).

The available information suggests that there is a strong correlation between islet allograft failure and a rise in anti-donor HLA sensitization as detected by panel reactive antibody (PRA) testing. Sensitization of T1D individuals may limit the number of compatible donor kidneys or other organs should a transplant be needed in the future.

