1.5.6 Procedures for Minimizing Risks

A number of features of the proposal have been designed to maximize the safety of subjects in the trial. Important selection criteria include avoidance of any medical condition that might significantly increase the risk related to islet transplantation. Importantly this includes selection of kidney recipients who have stable graft function and who are at a low risk for rejection of their graft. In addition, renal graft function in potential trial subjects has to be sufficient (CrCl of > 40 mL/min) so that it is unlikely that they will experience imminent graft failure and face the need for ongoing immunosuppression for an islet graft in the absence of a functioning kidney.

To ensure further that there is no detrimental impact on renal graft function, the maintenance immunosuppression regimen already in place for the renal graft will be continued without marked changes to benefit the islet transplant. This approach will avoid immunosuppressant drug changes that

could potentially precipitate renal allograft rejection.

In addition, the induction immunosuppression regimen based on rabbit ATG is well studied and has been demonstrated to have a favorable safety profile in solid organ transplantation. The islet preparation to be infused will be isolated from cadaveric donors thoroughly tested for transmissible infectious agents and will be free of recent high-risk behaviors. In addition, the islet product will be tested preinfusion to verify a suitable level of purity, viability, mass, and endotoxin.

Since gaining insulin independence is dependent on the recovery and infusion of a sufficient islet mass per recipient BW, the trial has been limited subjects < 100 kg in an attempt to maximize the likelihood that insulin independence will be achieved with one (or two) islet transplants. It is recognized that subjects ≥ 100 kg should benefit equally for this therapy should a sufficient islet mass be obtainable.

The informed consent process is carefully organized to minimize unrealistic expectations. We will also reject volunteer subjects who are so desperate as to be incapable of understanding and/or coping with the possibility of failure. We believe that our process leading to informed consent is purposefully organized so as to minimize psychological risk to the recipient.

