3. SELECTION AND WITHDRAWAL OF SUBJECTS

3.1 Inclusion Criteria

Subjects who meet *all* of the following criteria are eligible:

1. Male and female subjects age 18 to 70 years.
2. Subjects who are able to provide written informed consent and to comply with the procedures of the study protocol.
3. Subjects in the United States must have one of the following payment mechanisms in place:
 - a. Medicare,
 - b. A third-party insurer who agrees, via pre-authorization, to pay for participation in the study, or
 - c. Another mechanism of payment (self-pay, hospital, university, donations, etc.) for participation in the study.
4. Clinical history compatible with T1D with disease onset < 40 years of age and insulin-dependence for ≥ 5 years at the time of enrollment.
5. Absent stimulated c-peptide (< 0.3 ng/mL) in response to a MMTT [Boost[®] 6 mL/kg body weight (BW) to a maximum of 360 mL; another product with equivalent caloric and nutrient content may be substituted for Boost[®]] measured at 60 and 90 min after start of consumption.
6. Subjects who are ≥ 3 months post-renal transplant who are taking appropriate calcineurin inhibitor (CNI) based maintenance immunosuppression ([tacrolimus alone or in conjunction with sirolimus, mycophenolate mofetil, myfortic, or azathioprine; or cyclosporine in conjunction with sirolimus, mycophenolate mofetil, or myfortic] \pm Prednisone ≤ 10 mg/day).
7. Stable renal function as defined by a creatinine of no more than one third greater than the average creatinine determination performed in the 3 previous months prior to islet transplantation, until rejection, obstruction or infection is ruled out.
8. Subjects who meet one of the options in the following criterion are eligible for transplantation:
 - Reduced awareness of hypoglycemia manifested by a Clarke score of 4 or more measured upon study enrollment and at least one episode of severe hypoglycemia in the 12 months prior to study enrollment.

OR

 - a subject must have a reduced awareness of hypoglycemia manifested by a Clarke score of 4 or more and at least 1 episode of severe hypoglycemia;

OR

 - Any subject not meeting the hypoglycemia option must have an HbA1c $\geq 7.5\%$.

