5.8.2 Modification of Standard Immunosuppression

ISLETS ARE UNSUITABLE

Should an islet product become unsuitable for transplantation subsequent to induction immunosuppression, the subject will remain on maintenance therapy required for their renal transplant. This will provide sufficient time for organ procurement, islet isolation, and infusion of an islet product without any additional induction treatment to the recipient. An emergency request will be placed through UNOS that the next available pancreas for islet transplantation is directed to the selected manufacturing site. When an organ becomes available, investigators should defer to the MOP to determine the amount and type of induction immunosuppression that will be administered at the time of islet transplant.

GRAFT FAILURE

Subjects who experience islet graft failure will be maintained on their current immunosuppressive regimen for their renal graft as long as a subsequent islet transplant is possible. If/when it is determined that a subject will not receive a subsequent islet transplant, the subject will move to the reduced follow-up schedule.

ALLERGIC REACTION TO ATG

If a subject demonstrates an allergic reaction to thymoglobulin that results in cancellation of the initial transplant and the investigators feel that future use of the drug in the subject is contraindicated, the steps outlined should be followed. Once another organ becomes available, the subject will receive the alternate induction immunosuppressive regimen outlined in this protocol.

INTOLERANCE OF PROTOCOL MEDICATIONS

In the event that protocol-regulated concomitant medications are not tolerated, the subject will continue taking the immunosuppressive therapy in order to protect the islet and renal grafts. In the event that the immunosuppression regimen is not tolerated, the site PI may elect to prescribe an alternative immunosuppression regimen. The intent would be for the alternative regimen to be temporary in nature.

where possible and any such decision made with the primary interest of maintaining the function of the renal allograft. Any non-protocol directed study treatment modification that the site PI determines is necessary should be reported as a protocol deviation.

RABBIT ANTI-THYMOCYTE GLOBULIN-INDUCED ANAPHYLAXIS

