7.6.1 Second Islet Transplant Criteria

Islet transplant recipients with partial islet graft function (see Study Definitions) will be considered for a second islet transplant in the interim between 30 ± 3 days and 8 months post-initial infusion.

Islet transplant recipients with graft failure will be considered for a second islet transplant before 8 months post-initial infusion. Please refer to the MOP for details on this process, which includes review of the potency testing from the first transplant product and post-transplant clinical data.

In order to be eligible for a second islet transplant, the following requirements must be met:

1. Subject received \leq 5,000 IEq/kg with the first transplant, but failed to achieve or maintain insulin independence.
2. Subject has been compliant with study monitoring and prescribed immunosuppressive therapy.
3. No evidence of a serious and life-threatening infection, AE, or other condition that precludes attempting an intraportal injection or continuation of the post-transplant treatment regimen.
4. Subject has no unresolved SAEs.
5. No evidence of PTLD, requiring complete withdrawal from immunosuppressive therapy.
6. No evidence of hypersensitization, allergic responses, or other potentially serious drug reactions to medications required by the protocol.
7. Stable renal function as defined as being a creatinine of no more than one third greater than the average creatinine determination performed in the 3 previous months, until rejection, obstruction or infection is ruled out.
8. Absence of any medical condition that, in the opinion of the investigator, will interfere with a safe and successful second islet transplant.
9. Absence of anti-HLA antibodies directed to the kidney transplant or to the current islet preparation detected by Luminex Single Antigen/specificity bead assay (including weakly reactive antibodies that would not be detected by a flow cross-match). All kidney and currently-proposed islet preparation donor specificities must be avoided in 2nd and 3rd islet transplants.

If graft failure occurs after the second islet transplant, these recipients will be considered treatment failures and immunosuppression will be withdrawn.

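### Section 7.6.1 orders immunosuppression stopped when the islet graft fails after a second transplant, which contradicts Section 1.5.1.3 and, followed literally, endangers a working kidney transplant

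*Combined protocol and SAP*

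**What the plan says.** The closing sentence of Section 7.6.1 covers recipients whose graft fails after the second islet transplant: "these recipients will be considered treatment failures and immunosuppression will be withdrawn". The Study Definitions tie failure to the islets only: "Islet allograft failure will be defined as absence of insulin production by transplanted islets, as evidenced by c-peptide" below 0.3 ng/mL, first on a random test and then throughout a mixed-meal test.

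Other sections state what happens to the kidney's drugs:

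- **Section 3.1** admits only kidney recipients "who are taking appropriate calcineurin inhibitor (CNI) based maintenance immunosuppression".
- **Section 1.2** justifies this population because "they are already obligated to chronic life-long immunosuppression".
- **Section 1.5.1.3** says that "patients with kidney transplants will continue taking maintenance immunosuppressive medications even if the islet graft fails". It describes stopping the drugs as usual practice in islet-alone patients.
- **Section 1.5.6** says the "maintenance immunosuppression regimen already in place for the renal graft will be continued without marked changes to benefit the islet transplant", to avoid drug changes that "could potentially precipitate renal allograft rejection".
- **Section 5.8.2 (Graft Failure)** keeps subjects on their regimen "for their renal graft as long as a subsequent islet transplant is possible". After that they go to reduced follow-up, and nothing is said about their drugs.

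**The concern.** The operative section gives an unqualified order that the risk section says will not be carried out. A site that follows 7.6.1 to the letter would stop the drugs protecting a functioning kidney because a different graft had failed. Losing that kidney could be irreversible, and it is the harm that Section 1.5.6 says the protocol is designed to avoid.

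There are two further consequences. Section 1.5.1.3 estimates additional sensitization at about 5-10% for islet-after-kidney patients who stay on maintenance drugs; withdrawal removes the condition on which that estimate rests. Also, any kidney lost this way would count in the renal allograft survival measure (Sections 4.1.2 and 9.1.10), which is compared with CIT-06 controls. The documents do not say whether CIT-06 had the same rule, so the direction of any bias in that comparison is unknown.

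**Working it through.** The plan states no figure on this point. The check is a comparison of sections, with one small calculation.

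**1. Does the order reach subjects with a working kidney?** Yes. All subjects are kidney recipients (3.1). Failure is defined by c-peptide, and kidney status plays no part in it. The definition of treatment failure is simply graft failure after the second islet transplant; it says nothing about stopping drugs.

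**2. What immunosuppression is left to withdraw?** There is no separate islet maintenance regimen: the Synopsis and Section 4 keep subjects on the calcineurin-based regimen they already take. The drugs added for a transplant are short courses:

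| Drug | Last scheduled day | Source |
|---|---|---|
| ATG (first transplant only) | +2 | 5.3.1, Table 1 |
| Basiliximab (later transplants) | 4 | 5.3.2 |
| Etanercept | +10 | 5.4.1 |
| AAT | 21 | 1.3.1 |

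Section 7.5 sets at least 36 months of follow-up after the last transplant, about 3 × 365 = 1,095 days.

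- Through etanercept: 10 / 1,095 = 0.9%.
- Through AAT: 21 / 1,095 = 1.9%.

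For the remaining 98.1% to 99.1% of that time, the kidney's maintenance regimen is the only immunosuppression the protocol schedules. This is a share of calendar time, not of failures; the documents do not say when failures occur.

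**3. Do other sections agree with 7.6.1?**

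- 1.5.1.3 contradicts it directly.
- 1.5.6 conflicts with it mainly in purpose. Its wording concerns changes made for the islets' benefit, but its stated reason is to protect the kidney from drug changes.
- 5.8.3 mentions ending chronic immunosuppression only where the kidney has been lost and the subject chooses to stop.

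**4. Does any section override it?** No. The protection in 5.8.2 lasts only while another islet transplant is possible. Section 7.6.2 requires partial islet function one month after the second transplant and closes eligibility 8 months after the first. A subject whose graft has failed by one month, or fails after the 8-month limit, has no protection under 5.8.2. A subject with partial function at one month who fails later, but inside the limit, could still meet that item, so the protection lapses for most of these subjects but not necessarily all.

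**5. Would monitoring catch the harm?** Poorly. Appendix 2 asks about SAEs at each contact and collects alloantibody, but it measures serum creatinine only at 1, 2 and 3 years after the final transplant. It has no calcineurin level and no medication review.

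**The case against.** The strongest reply is that *immunosuppression* in 7.6.1 means only the study drugs. Table 1 and Section 5.3 use the word for the peri-transplant drugs, while the kidney's drugs are usually called maintenance immunosuppression. In primary non-function (days 3 to 7), basiliximab and etanercept doses may still be due, so withdrawal would then mean something. This reading is possible, but 7.6.1 does not state it, and it leaves the order empty for any failure after the first days.

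A second reply is that the protocol elsewhere puts the kidney first. Changes for intolerance must serve renal graft function (5.8.2), CNI changes for nephrotoxicity belong to the physician managing the kidney, and drug targets are left to the transplant physician (Sections 4 and 7.4). That shows intent, and an experienced physician would probably not follow 7.6.1 literally. None of these provisions overrides it, however, and a physician who sensibly continued the drugs would arguably be departing from the protocol.

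A third reply is that few people are affected. Twenty subjects are to be transplanted, and the rule applies only to those who have a second transplant and then lose all islet function. That stands. The case for correction rests on the seriousness of the harm, not its frequency.

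**Conclusion.** The concern holds. Section 7.6.1 directly contradicts Section 1.5.1.3, runs against the purpose of Section 1.5.6, and is not cured by 5.8.2. It is most likely a drafting error, but as written it instructs sites to do something unsafe and must be corrected.

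The rule covers every subject whose islet graft fails after a second transplant. No size of harm can be given, because the documents supply neither the number of such failures nor a kidney loss rate. Harm also requires a site to apply the sentence literally. Renal allograft survival, the outcome exposed, is neither the primary nor the key secondary endpoint. The sample size and the day-75 primary analysis are not shown to be affected.

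**What to change.** Replace the closing sentence of Section 7.6.1 with text to this effect: *Recipients whose islet graft fails after the second transplant are treatment failures and receive no further islet transplants; maintenance immunosuppression for the kidney allograft continues as directed by the physician managing the renal transplant.*

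Add the same statement to the Graft Failure paragraph of Section 5.8.2, so that it covers the period once no further islet transplant is possible. This puts into the operative sections what 1.5.1.3 and 1.5.6 already imply.

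The cost is two sentences by amendment, with no change to sample size, visits or analysis. Optionally, add one field to Appendix 2 for the date of any change in maintenance immunosuppression. It would be collected at existing contacts, at small added cost.

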7.6.2 Third Islet Transplant Criteria

The option of a third islet transplant under this protocol will be considered only if all of the following conditions are met:

1. The subject received greater than 4,000 IEq/kg following the second transplant, but remains dependent on insulin for longer than one month after the second transplant.
2. There is evidence of partial islet graft function at one month.
3. The Protocol Chair, and the Site Principal Investigators (PIs), determined that there were no relevant protocol deviations at the site.
4. The subject has been compliant with study monitoring and prescribed immunosuppressive therapy.
5. No evidence of a serious and life-threatening infection, AE, or other condition that precludes attempting an intraportal injection or continuation of the post-transplant treatment regimen.
6. Subject has no unresolved SAEs.
7. No evidence of PTLD, requiring complete withdrawal from immunosuppressive therapy.
8. No evidence of hypersensitization, allergic responses, or other potentially serious drug reactions to medications required by the protocol.
9. Stable renal function as defined as being a creatinine of no more than one third greater than the average creatinine determination performed in the 3 previous months, until rejection, obstruction or infection is ruled out.
10. Absence of anti-HLA antibodies directed to the kidney transplant or to the current islet preparation detected by Luminex Single Antigen/specificity bead assay (including weakly reactive antibodies that would not be detected by a flow cross-match). All kidney and currently-proposed islet preparation donor specificities must be avoided in 2nd and 3rd islet transplants.

Subjects who have completed 8 months follow-up post-initial transplant will no longer be eligible for additional islet transplants funded under this protocol.

